2.3.3 Vital signs

Descriptive statistics will be provided for values and change from baseline at each assessment time point for systolic blood pressure, diastolic blood pressure, pulse, respiratory rate, body temperature, and weight.

Blood pressure and pulse during 48 hours drug infusion and 48 hours post infusion will also be listed.

2.3.4 Electrocardiogram (ECG)

An ECG substudy will be conducted at a subset of selected sites to enroll at least 500 subjects. Subjects without written informed consent for the ECG substudy before any study-specific assessment is performed will be excluded from the population.

The analyses will be performed based on subjects who have at least one ECG at baseline (ECG recordings taken before the infusion starts will be considered) and one ECG post baseline (48 hour time point) which is recorded within 60 minutes after study drug infusion ends.

The following quantitative variables will be summarized: RR interval, PR interval, QRS duration, QT interval, and corrected QT interval (QTc).

The number and percentage of subjects with the following criterion will be presented.

- QT > 500 msec
- QT > 480 msec
- QT > 450 msec
- QT > 450 msec, male only
- QT > 460 msec, female only
- QT increases from baseline > 30 msec
- QT increases from baseline > 60 msec
- PR > 200
- PR > 220 msec
- PR increases from baseline > 25%
- QRS > 110 msec and increase from baseline $\geq 25\%$
- QRS > 120 msec and increase from baseline $\geq 25\%$
- Heart rate > 100 beats per minute and increase from baseline $\geq 25\%$
- Heart rate < 50 beats per minute and decrease from baseline $\geq 25\%$

QT data will be analyzed for both the Fridericia (primary) and Bazett's (secondary) corrections.

Newly occurring abnormalities in ECG morphology will be summarized by treatment group and overall. Newly occurring is defined as no occurrence on any of the baseline ECGs with the presence of the finding on any single ECG post baseline.

A listing of all abnormalities will be provided, as well as a by-subject listing of all quantitative ECG parameters.

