In addition to the core study, ECG, laboratory and biomarker substudies will be conducted.

- At least 500 patients from selected centers will participate in an ECG substudy. ECGs will be performed at Baseline and at the end of study drug infusion.
- At least 1600 patients from selected centers will participate in a laboratory substudy. Safety laboratories will be collected at Baseline, daily while hospitalized up to Day 5, Discharge and Day 14. Patients discharged prior to Day 5 will return to the hospital/clinic for Day 5 procedures.
- At least 1600 patients from selected centers participating in the laboratory substudy will also participate in the biomarker substudy. Biomarkers will be collected at Baseline, Days 2, and 5, Discharge, and Day 14. Patients discharged prior to Day 5 will return to the hospital/clinic for Day 5 procedures.

Based on sample size calculations based on RELAX-AHF, approximately 6,800 randomized AHF patients will be required to accrue the number of events during the 180-day follow-up

period necessary to reach the primary efficacy endpoint. Once randomized, all randomized patients will be followed to 180-day.

There will be one interim analysis at 60% of the accrued numbers of confirmed CV deaths (see details in [Section 10.6](#) and [Section 10.7](#)). If following the interim analysis, the trial is concluded early for efficacy, all ongoing randomized patients will be followed for 180 days.

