**Table 5-4 Dosing adjustment of study drug administration in the event of systolic BP decrease**

Changes in systolic BP during infusion*	Adjustments of study drug administration
Decrease >40 mmHg from pre-treatment at baseline, but systolic BP remains $\geq$ 100 mmHg	Reduce the infusion rate by half for the remainder of the study drug administration, i.e., reduce infusion rate from 10 mL/hour to 5 mL/hour for the remainder of 48-hour infusion
Decrease in absolute systolic BP to <100 mmHg	Permanently terminate study drug infusion

\* These systolic BP values should be confirmed by two measurements taken 15 minutes apart

In addition, dosing may be discontinued at any time at the discretion of the investigator. Reasons the investigator may discontinue study drug administration include, but are not limited to, serious or intolerable AEs suspected to be related to study drug. If dosing is discontinued for systolic BP decreases, or any safety reasons, it should not be restarted. Re-administration of study drug once terminated for safety reasons is not allowed. The total time from initiation of study drug infusion to completion must not exceed 48 hours. In the event that study drug administration is discontinued, regardless of the reason, the patient will continue to be followed at all study visits defined in the protocol.

Changes in study drug dose must be recorded on the Dosage Administration Record CRF.

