k Blood will be collected in a subset of randomized patients participating in the laboratory substudy for measurement of biochemistry, hematology, and plasma HbA1C by the central laboratory. Following randomization, central laboratory collections can be adjusted to conform to the hospital's routine laboratory collection schedule and can be collected at any time of day. Baseline collection can be done at screening at the same time as the local laboratory collections. Urine dipstick will be measured locally at screening to rule out any conditions requiring further diagnostic evaluation or treatment. Refer to [Section 6.5.4.3](#)

l Blood will be collected in a subset of randomized patients participating in the biomarker substudy to be performed by the central laboratory. Following randomization, biomarker substudy laboratory collections can be adjusted to conform to the hospital's routine laboratory collection schedule and can be collected at any time of day. Refer to [Section 6.6.6](#)

m Non-serious AEs and SAEs will be reported from the signing of the ICF through Day 5 and 14, respectively.

n ECGs will be collected in a subset of randomized patients participating in the ECG substudy and sent to a central ECG vendor for evaluation. ECGs will be collected at Baseline and at the end of study drug infusion. Refer to [Section 6.5.5](#).

o Major cardiovascular and non-cardiovascular classes of medication taken by a subject approximately 30 days prior to study drug initiation and on a daily basis while hospitalized through Day 5, at Discharge, and at Days 14, 60, 120 and 180 will be recorded. Only those medications currently being taken or that were taken within 24 hours prior to the visit will be collected.

p Withdrawal of consent form is only completed when a patient does not want to participate in the study any more and, does not want any further visits or assessments and, does not want any further study related contacts and does not allow analysis of already obtained biologic material..

q ECGs will be performed and interpreted locally at screening and at Day 5 or discharge, whichever occurs first. The ECG interpretation and person interpreting the ECG must be recorded in the source documents

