### **6.5.5.2 ECG substudy**

At least 500 patients from selected centers will participate in a substudy to evaluate the impact of serelaxin on ECGs values. All patients at a selected center will be asked to participate in the substudy until all 500 patients have been enrolled. A standard triplicate 12-lead ECG will be performed at baseline and at the end of study infusion and sent to a central ECG vendor for interpretation. Each ECG tracing should be labeled with the study and patient number, patient

initials (if applicable), date, and kept in the source documents at the study site. Clinically significant abnormalities should also be recorded on the Medical History/Adverse event CRF page.

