Table 2-5 Primary, secondary and exploratory variables	15
Table 2-6 IV loop diuretics.....	23
Table 2-7 Safety risk and event of interest search specification	27
Table 2-8 Criteria for evaluating liver toxicity.....	31
Table 2-9 Nominal one-sided alpha at 70% randomized subjects accrued if CVD is rejected	34
Table 2-10 Assumed effect sizes for worsening heart failure and the key secondary efficacy variables on power calculation.....	36
Table 2-11 Powers (unconditional) of primary and key secondary variables on selected scenarios	36

Document History – Changes compared to previous version of RAP module 3.

Version	Date	Changes
Amendment 1	13-Aug-2015	
 -add the testing strategy for WHF and secondary endpoints in case of early stopping -add sensitivity analysis for WHF using logistic regression -add substudy population definition
Amendment 2	06-Feb-2017	
 - Clarify the method of mapping discharge visit to scheduled visits if scheduled visits are missing - Update the list of countries that recruited subjects (Table 2-3) - Remove subgroup category of lymphocytes and education level in Table 2-4 - Use FAS in section 2.1.9 – study medication summary. - Align presentation of non-IV concomitant medications with RELAX-AHF - Clarify definition of the censoring date for death endpoints (Adjudicated CV death, adjudicated all cause death) for patients who withdrew consent in countries where vital status data is publically available, in accordance with local laws and regulations - Clarify use of discharge date as the reference date for endpoint time to the composite endpoint of CV death or rehospitalization due to HF/RF during a follow-up period of 30 days post-discharge - Clarify the statistical method used for subgroup analysis of length of stay (LOS). Clarify the imputation rule for missing discharge information to align with RELAX-AHF - Clarify the imputation of signs and symptoms through Day 5 for subjects with WHF or died at hospital to align with RELAX-AHF - Addition of two new tables per ClinicalTrials.gov and EudraCT requirement -Update Safety risk and event of interest search specification (Table 2-7) - Clarify the ECG analysis population - Update the ECG categorical analysis, add analysis of newly occurring abnormalities in ECG morphology and remove ECG shift table to enable comprehensive assessment - Update liver function categorical analysis (Table 2-8)

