The CRLX030A2301 study (also referred to as RELAX-AHF-2) aims to evaluate the efficacy, safety and tolerability of intravenous infusion of 30 µg/kg/day serelaxin for 48 hours, when added to standard therapy. Data from this study is intended to replicate the reduction in mortality in AHF patients observed in the RELAX-AHF study.

The purpose of this document is to outline the planned analyses to be completed to support the completion of the Clinical Study Report (CSR) for RELAX AHF-2.

2 Statistical methods planned in the protocol and determination of sample size

Data will be analyzed according to the data analysis section 10 of the study protocol which is available in [Appendix 16.1.1 of the CSR](#).

All nominal time points will be used for analysis; actual assessment times will not be used to reclassify the time point at which a measure was taken. Time-to-event analyses will be based on actual dates (time) reported.

All references to index hospitalization refer to the initial hospitalization for AHF.

Unless specified, descriptive statistics indicates mean, median, standard deviation, minimum and maximum will be presented for continuous variables; the number and percentage of subjects in each category will be presented for categorical variables for each treatment group and all subjects (total).

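### The SAP's ECG rule opens its window only when the infusion stops, so a protocol-compliant ECG taken just before the stop removes the subject from every ECG summary

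*SAP*

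**What the plan says.** The protocol describes one post-baseline recording for the ECG substudy and gives its timing in three places.

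- Protocol 3.1: "ECGs will be performed at Baseline and at the end of study drug infusion".
- Protocol Table 6-1, footnote n: "ECGs will be collected at Baseline and at the end of study drug infusion".
- Protocol 6.5.5.2: "A standard triplicate 12-lead ECG will be performed at baseline and at the end of study infusion".

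None of them gives a tolerance in minutes or says that the infusion must be stopped before the recording.

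SAP 2.3.4 decides who enters the ECG analyses. At baseline the rule is open: "ECG recordings taken before the infusion starts will be considered". After baseline the subject needs "one ECG post baseline (48 hour time point) which is recorded within 60 minutes after study drug infusion ends". The SAP provides no allowance before the stop and no analysis without the restriction. The SAP's document history lists this population among the Amendment 2 changes: "Clarify the ECG analysis population".

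Two other statements bear on the 48-hour label. Protocol 5.5.5 caps the infusion: "The total time from initiation of study drug infusion to completion must not exceed 48 hours". SAP section 2 sets a nominal-time convention for the analyses: "actual assessment times will not be used to reclassify the time point at which a measure was taken".

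**The concern.** The SAP window is one-sided and the protocol instruction is not. A site that records the triplicate in the last minutes of the infusion has done what the protocol asks, yet the subject fails the SAP criterion. Because the criterion selects subjects rather than tracings, that subject is lost to every ECG summary, not only to the QT tables.

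This is the trial's only centrally read ECG assessment. The local ECGs in Protocol 6.5.5.1 are interpreted on site and kept in source documents. The sponsor lists QT prolongation as an event of interest in SAP Table 2-7, so usable recordings made while drug is being delivered should not be discarded without a stated reason.

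A second question is what the 48-hour label means for an infusion that ends early. If it is a condition on clock time, the rule selects on an event after randomization. Protocol 3.1 names hypotension as a potential risk of the study drug, and blood pressure falls can end the infusion, so treatment could influence that event.

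**Working it through.** The plan states no precision, power or expected yield for the ECG analysis, so there is no figure of its own to reproduce. The check has three parts.

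**1. The window applied literally.** Let t be the ECG time in minutes from the infusion stop. The SAP rule is 0 ≤ t ≤ 60.

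| t (min) | Consistent with the protocol's timing | Meets the SAP rule |
|---|---|---|
| −60 | not defined (no window given) | no |
| −30 | not defined | no |
| −10 | yes, on an ordinary reading | no |
| −1 | yes | no |
| 0 | yes | yes |
| +30 | not defined | yes |
| +60 | not defined | yes |
| +61 | not defined | no |

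An ECG at exactly hour 48 of a full infusion falls on the edge and is kept. Where a triplicate straddles the stop, the subject qualifies, and the SAP does not say that the earlier tracings are removed.

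**2. The 48-hour label when the infusion ends early.** Let s be the stop time in hours, with s ≤ 48 under Protocol 5.5.5. An ECG at clock hour 48 is 48 − s hours after the stop, so it is within 60 minutes only if s ≥ 47. Take s = 20:

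- An ECG at the stop is at hour 20. It meets the 60-minute limit but is not at clock hour 48.
- An ECG at clock hour 48 is 48 − 20 = 28 hours after the stop and fails the 60-minute limit.

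If the label is a clock-time condition, no ECG from this subject qualifies, and the same holds for any s below about 47. If it is only a visit label, the ECG at hour 20 qualifies.

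**3. Illustrative cost in precision.** From the documents: at least 500 subjects (SAP 2.3.4) and 1:1 allocation (Protocol 5.2). Assumed: exactly 500 subjects, an SD of 20 ms for change in QTcF, and a share f of subjects whose only end-of-infusion ECG came before the stop. Neither the SD nor f is in the documents.

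With n = 250 × (1 − f) per arm, the 95% half-width for the arm difference is 1.96 × 20 × √(2/n). The approximate upper 95% bound on a rate with zero events in one arm is 3/n.

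| f | Total | n per arm | Half-width (ms) | 3/n |
|---|---|---|---|---|
| 0 | 500 | 250 | 39.2 × √(2/250) = 3.5 | 1.2% |
| 10% | 450 | 225 | 39.2 × √(2/225) = 3.7 | 1.3% |
| 20% | 400 | 200 | 39.2 × √(2/200) = 3.9 | 1.5% |
| 40% | 300 | 150 | 39.2 × √(2/150) = 4.5 | 2.0% |

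SAP 2.3.4 plans summaries and counts, not a formal comparison of arms. The half-width is therefore only a yardstick for lost information.

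**The case against.** The best defence is that the end of an infusion ordinarily means its completion, and that the 60 minutes is a sensible tolerance added on purpose in Amendment 2. The authors may even have meant it only as an upper limit. Site or central-vendor instructions outside these documents may fix the timing. This lowers the likely number of subjects affected. It does not change the text: the window starts at the stop, and the protocol does not require the infusion to be off.

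Several stronger inferences are tempting, and the objection to each is sound.

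- *The rule discards the recordings with full exposure, or the most informative ones.* No pharmacokinetic analyses are planned (Protocol 6.6.4), no half-life is given, and some subjects have their rate halved (Protocol Table 5-4). For assumed half-lives of 0.5 to 8 hours, the concentration 60 minutes after the stop would be 25% to 92% of the value at the stop, which is anything from a large drop to a small one. The documents support only that drug is being delivered before the stop and is not afterwards.
- *The rule biases the arm comparison.* Treatment is double-blind, so recording a little before the stop should be about equally common in both arms. That costs precision and does not by itself bias the difference.
- *Early stoppers are certainly excluded.* A stop at 47 h 30 min leaves hour 48 inside the window. For earlier stops, exclusion follows only if the 48-hour label is a condition. The SAP's nominal-time convention favours reading it as a visit label.
- *Table 6-1 shows that the Hour 48 visit takes place with the infusion running.* The extracted table is broken, and hour 48 is in any case the planned end of the infusion.

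It is also true that clinically significant ECG abnormalities are recorded on the medical history or adverse event pages, that QT and arrhythmia terms are searched in the safety set, and that SAP 2.3.4 plans by-subject listings. These soften the loss. They do not replace the central interval summaries and outlier counts.

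**Conclusion.** The point holds on the wording of the two documents. SAP 2.3.4 excludes a subject whose only end-of-infusion triplicate was taken shortly before the stop, although the protocol permits that timing, and nothing else in the plan brings the subject back into the summaries.

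The size is unknown because the share of such subjects is not in the documents. Under the assumptions above, a loss of 10% to 20% is modest and a loss of 40% is material: the half-width is 3.7, 3.9 and 4.5 ms for losses of 10%, 20% and 40%, against 3.5 ms with none. The cost is precision, not a demonstrated bias toward missing a QT effect.

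Selection on early stopping is a separate, conditional problem. It arises only if the 48-hour label is applied as a clock-time requirement, and the SAP should rule that reading out.

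**What to change.** In SAP 2.3.4:

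1. Define the qualifying post-baseline ECG relative to the actual end of infusion, whenever that occurred, with a window that also admits recordings shortly before the stop. An example is 60 minutes before to 60 minutes after. The exact lower bound is the sponsor's choice, but it must be stated.
2. Say that the 48-hour wording is only the nominal visit label, or delete it.
3. Add a sensitivity table of all available post-baseline substudy ECGs regardless of window.

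The change should be made before unblinding. It takes a short edit and one extra table. No new ECGs are needed, and the present rule already requires both the ECG time and the infusion stop time. The downside is slightly more variable timing relative to the stop in the main ECG set, which the sensitivity table does not remove, so the distribution of recording times relative to the stop should be reported by arm.

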### **5.2 Treatment arms**

Patients will be randomized in a 1:1 ratio to receive continuous intravenous infusion of one of the following treatment assignments for 48 hours:

- Placebo
- Serelaxin (30 µg/kg/day)

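### The SAP prespecifies no between-arm QTc difference with a confidence interval for the ECG substudy and does not adjust for the baseline QTc it collects; adding both is a minor, nearly free improvement

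*SAP*

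**What the plan says.** Protocol 6.5.5.2 gives the substudy a comparative purpose: "At least 500 patients from selected centers will participate in a substudy to evaluate the impact of serelaxin on ECGs values". On measurement it says: "A standard triplicate 12-lead ECG will be performed at baseline and at the end of study infusion". The tracings are read by a central vendor. Allocation in the trial is 1:1 (Protocol 5.2).

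SAP 2.3.4 repeats the size of at least 500. It restricts the analysis to patients with a pre-infusion ECG and "one ECG post baseline (48 hour time point) which is recorded within 60 minutes after study drug infusion ends". For continuous variables the plan is: "The following quantitative variables will be summarized: RR interval, PR interval, QRS duration, QT interval, and corrected QT interval (QTc". The SAP's general rule in section 2 is that "descriptive statistics indicates mean, median, standard deviation, minimum and maximum will be presented for continuous variables", by treatment group and in total.

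The rest of SAP 2.3.4 consists of counts and percentages over cut-offs (including QT increases above 30 and above 60 ms), newly occurring morphology abnormalities by treatment group, and listings. Fridericia is named as the primary correction and Bazett as the secondary one. No between-arm estimate, interval, test or model is named.

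Protocol 10.5.2 describes no ECG analysis. The only QT-related between-arm interval is the odds ratio with 95% CI in SAP 2.3.1 for events found by the QT-prolongation search in Table 2-7. That concerns reported adverse events, not measured QTc.

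**The concern.** The substudy asks about a treatment effect and has a randomized placebo control, but the planned output stops at by-arm summaries and counts. The direct answer would be the difference between arms in QTcF at end of infusion, with an interval showing which effects the data rule out. The plan does not commit to that number.

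The baseline QTc is collected in triplicate, yet it enters only through the cut-offs on increase from baseline. It is not used as a covariate. The SAP does not say that change from baseline will be summarised for continuous QTc, or how the three readings will be combined.

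The plan does more elsewhere. Protocol 10.5.2 compares changes in vital signs between arms by t-test, and SAP 2.2.7.3 fits a baseline-adjusted repeated-measures model to biomarkers. At stake are the clarity and precision of one safety result, and whether the estimate is fixed in advance or chosen after unblinding.

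**Working it through.** **Nothing to reproduce.** The documents give the substudy size of 500 without an SD, effect size, error rate or target precision.

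**Inputs from the documents:** at least 500 patients (Protocol 6.5.5.2, SAP 2.3.4) and 1:1 allocation (Protocol 5.2), so about n = 250 per arm if the substudy follows the main trial.

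**Assumed inputs, not in the documents:** SD of QTcF 20-30 ms; correlation r between baseline and end-of-infusion QTcF 0.5-0.7; all 500 evaluable. Wider ranges follow below.

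**Precision of the mean difference.** The factor √(2/250) is 0.0894.

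- Post-infusion values only: SE = SD × 0.0894
- Raw change from baseline: SE = SD × √(2(1−r)) × 0.0894
- ANCOVA on baseline: SE = SD × √(1−r²) × 0.0894

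Example, SD 30 and r 0.5: raw change 30 × 1 × 0.0894 = 2.68, times 1.96 = 5.3 ms; ANCOVA 30 × 0.866 × 0.0894 = 2.32, times 1.96 = 4.6 ms.

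| SD (ms) | r | Post only, 95% half-width | Raw change | ANCOVA |
|---|---|---|---|---|
| 20 | 0.5 | 3.5 | 3.5 | 3.0 |
| 20 | 0.7 | 3.5 | 2.7 | 2.5 |
| 30 | 0.5 | 5.3 | 5.3 | 4.6 |
| 30 | 0.7 | 5.3 | 4.1 | 3.8 |

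The ratio of ANCOVA variance to raw-change variance is (1−r²)/(2(1−r)) = (1+r)/2, which is 0.75 at r = 0.5 and 0.85 at r = 0.7. The saving is therefore 15-25%. With 90% intervals the half-widths are 2.1-3.8 ms (ANCOVA) and 2.3-4.4 ms (raw change).

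**Power for a true 10 ms shift, two-sided 5%.** The categories depend on the SD of the change, so the comparison is made at a change SD of 20 and 30 ms. These equal the QTcF SD when r = 0.5. Category proportions come from a normal distribution of change with mean 0 or 10 ms; for example, with SD 20, P(change > 30) = P(Z > 1.5) = 6.7% against P(Z > 1.0) = 15.9%.

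| Measure | Change SD 20 | Change SD 30 |
|---|---|---|
| Mean difference, raw change | over 99% | 96% |
| Mean difference, ANCOVA (r = 0.5) | over 99% | 99% |
| Increase > 30 ms: proportions | 6.7% → 15.9% | 15.9% → 25.2% |
| Increase > 30 ms: power | 90% (Fisher exact 89%) | 74% (Fisher exact 71%) |
| Increase > 60 ms: proportions | 0.1% → 0.6% | 2.3% → 4.8% |
| Increase > 60 ms: power | 14% (Fisher exact 0.4%) | 33% (Fisher exact 25%) |

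The 14% is an artefact of the normal approximation: the expected counts in that cell are about 0.3 and 1.6 patients per arm.

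**Wider assumptions.** With SD 40 ms and 250 per arm, the ANCOVA 95% half-width is 5.0-6.1 ms and power for 10 ms is 90-98%. With only 175 evaluable per arm and SD 20-40 ms, the half-width is 3.0-7.3 ms.

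**The case against.** The strongest case against is that the information is largely there already. Under the SAP's default, mean and SD are shown for each arm side by side. From n, mean and SD anyone can compute the randomized post-infusion difference and its unadjusted interval, and SAP 2.3.4 also lists every patient's quantitative ECG values. **This stands.** A reader might infer that the substudy cannot say whether serelaxin changes QTc; the documents do not support that. What is missing is a prespecified estimate. The by-arm summaries also do not yield a baseline-adjusted one.

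Second, a reader might infer that the planned categories are too weak to carry the question. That holds for increases above 60 ms but not for increases above 30 ms, which have about 74-90% power on the same assumptions. **This stands.**

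Third, baseline adjustment adds only modestly to a simple difference in change: 0.2-0.7 ms on the 95% half-width. Raw change already reaches 96% power or more for 10 ms at these SDs. **This stands:** the main gain comes from stating the between-arm difference at all, and ANCOVA is an efficiency refinement at no cost.

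Fourth, descriptive safety reporting is this SAP's general approach, the safety objective is general, and no ECG hypothesis or margin is declared. This is a fair reason to rate the point low. It does not remove it, because this is a dedicated substudy with an explicit effect question.

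Fifth, SAP 2.3.1 plans an odds ratio for QT-prolongation events. That is a randomized comparison, but of reported events, so it does not supply the measured QTc difference.

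**Conclusion.** The point holds as a minor, optional-level improvement. SAP 2.3.4 prespecifies no serelaxin-minus-placebo estimate with an interval for measured QTc, and it does not use the baseline QTc in any such estimate, although Protocol 6.5.5.2 poses a treatment-effect question. No other section of either document fills the gap.

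The planned data would support an interval of about ±2.5 to ±4.6 ms with ANCOVA. That precision rests on assumed SDs and correlations and on 250 evaluable patients per arm. The ordering of the methods is firmer than the figures: ANCOVA is never less precise than raw change under these formulas, and for a 10 ms shift the mean comparison is more powerful than either increase category examined.

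Two limits remain under any analysis. There is a single post-baseline time point, and the analysed subset is defined after randomization by having a usable ECG within 60 minutes of the end of infusion. No primary or key secondary conclusion depends on this.

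**What to change.** Add to SAP 2.3.4, before unblinding:

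- Change in QTcF from baseline to end of infusion, using the mean of the triplicate at each time, analysed by ANCOVA with treatment and baseline QTcF.
- The serelaxin-minus-placebo difference with a two-sided CI: 95% to match the SAP's other intervals, or 90% if the sponsor prefers.
- The same analysis for heart rate, PR and QRS.
- The threshold categories kept as supportive.
- The number of patients per arm excluded for lack of an ECG within 60 minutes of infusion end.

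The cost is a few lines of text and one table. No new data, visits or patients are needed.
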